NEW Tx is a flexible modular treatment such that modules are selected based on the needs of the individual to increase its generalizability across patients, settings, and providers as well as its acceptability to patients. The three modules of the intervention are as follows:

A. Nutrition/Weight Loss Module

To enhance nutrition, we review nutritious foods (e.g., high in vitamins and minerals, low in fat) in each of the food groups as well as teach participants how to calculate serving size to enhance portion control. We discuss the importance of a “balanced diet” as well as having essential vitamins and minerals, particularly ones that may be beneficial for mood disorders. Finally, we review food that may be unhealthy and why. Weight loss is tracked as needed and food diaries are used as needed (at minimum at baseline, week 10, and week 20) to monitor participants’ daily foods consumed and calories. Participants, with guide from their NEW Tx therapist, will determine a daily goal for caloric intake to assist in identifying healthy and realistic weekly weight loss goal. We utilize Cognitive Behavioral Therapy (CBT) strategies to challenge negative thoughts about changing food choices⁴⁴. We also include a session on emotional eating, or eating to cope with negative affect, by evaluating the accuracy of thoughts associated with the craving. We discuss positive coping strategies, or distraction activities, to replace food as a way to improve mood or “comfort” oneself. We also utilize the philosophy from Brownell’s LEARN program⁴⁵ that there are no “forbidden foods” as evidence suggests that this may increase cravings for these foods as well as negative thoughts about the module⁴⁶. We use psychoeducational materials to enhance adherence. We specifically discuss the impact of “psychological factors” and review research studies of diet programs that have had positive outcomes in severe mental illness. Finally, we employ behavioral strategies in NEW Tx, such as positive reinforcement, to enhance adherence through the use of reward charts. We then collaboratively set homework and weekly goals each session.

B. Exercise Module

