This module is integrated throughout the first two modules as it reinforces the importance of making healthy decisions (e.g., food choices, exercise, increasing behavioral activation) and helps to problem solve obstacles to making these choices. This module is reflected in the use of CBT-based strategies that focus on increasing adherence to the nutrition and exercise modules as well as other healthy choices (e.g., reduction of caffeine, smoking, substance use). For example, we discuss that having 5 to 6 smaller meals throughout the day is an ideal meal plan as it is healthier and enhances their routine and energy level, opposed to using caffeine or smoking as stimulants. We focus on these other lifestyle choices as exercise reduces the craving for smoking⁵¹ and substance use⁵² as well as seems to buffer against substance abuse⁵³.

Similarly, we encourage participants to choose a feasible time every other day to exercise and to use positive rewards when meeting exercise and diet goals. In this module, we also discuss important aspects of behavioral activation, such as balancing mastery and pleasurable tasks and setting appropriate mood-dependent schedules. An important aspect of enhancing healthy lifestyle choices is accounting for mood-specific shifts in their activation. For example, during (hypo)manic episodes bipolar individuals tend to be impulsive and overly energetic, and thus their lifestyles often become chaotic and erratic. In contrast, during depressive episodes, bipolar individuals lose this behavioral activation and thus, tend to isolate or withdraw. In this module, we stress the importance of having two feasible choices or plans: one for elevated moods and one for depressed moods. Both plans emphasize structure and healthy coping behaviors, but the activities vary. We also use reward charts to reinforce healthy decisions and challenge self-defeating thoughts (e.g., “I can’t change”). This module also incorporates motivational interviewing techniques which are effective in helping individuals gain insight into their unhealthy behaviors and the need for change⁵⁴.

IV. RESEARCH DESIGN AND METHODS

A. Overview

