An EKG will be required for participants over the age of 40, if clinically indicated, to further minimize potential risks associated with exercising. For clinical monitoring and assessment of adverse events, a fasting blood draw will be conducted at Week 0, Week 10, and Week 20. For the waitlist group (i.e., TAU participants who choose to receive NEW Tx after 20 weeks), fasting blood draws will be conducted at Weeks 30, Week 40, and Week 52, in addition to the aforementioned draws. Drug screens will not be required; however, administration of drug screening as part of ongoing treatment is at the discretion of the treating physician at any time after consultation with the participant.

C. Diagnostic and Clinical Assessments

- i. **Extended Mini-International Neuropsychiatric Interview** (MINI⁵⁷) will be used to establish DSM-IV diagnoses including BD, substance use, and eating disorders.
- ii. **Demographics, Medical History, and Psychiatric History** forms will assess any pertinent medical or psychiatric conditions that may impact the participants' eligibility or treatment in this study.
- iii. **Montgomery Asberg Depression Rating Scale** (MADRS⁵⁸) is a 10-item clinician-rated measure of depression that assesses the presence and severity of patient's current depressive symptoms.
- iv. **Young Mania Rating Scale** (YMRS⁵⁹) is an 11-item, clinician-rated measure that assesses the presence and severity of patient's current symptoms of mania.
- v. **Clinical Global Impression-Bipolar Illness** (CGI-BP⁶⁰) is a one item illness severity score that is a widely accepted, reliable, and valid assessment of global illness in BD⁶¹. The CGI-BP is a modified version of the CGI designed specifically for use in assessing global illness severity in patients with BD. This version assigns ratings for mania, depression, overall severity, and side effects.
- vi. **Clinical Monitoring Form** (CMF) Medication Module⁶² will track medication and dosage changes and whether the subject is taking medications for blood pressure (used to calculate the FSR score).
- vii. **Food Diaries** or a self-report record of foods and calories consumed will be completed by participants between study visits as needed. Selected food diaries will be reviewed by a dietitian (as needed).

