- viii. **Exercise Questionnaire** (EQ) is a modified version of the Exercise History and Attitude Questionnaire which has been used in a wide variety of settings^{63, 64}. It is typically administered to healthy populations; thus, some items were excluded that were not likely to pertain to BD. This questionnaire assesses baseline (i.e., past) exercise history as well as ongoing exercise duration and frequency at follow-up study visits⁶⁵.
- ix. **LIFE- Range of Impaired Functioning Tool** (LIFE-RIFT^{66, 67}) assesses the extent to which medical burden has impacted current functioning.
- x. **Framingham Risk Score** (FRS) will be used to estimate medical burden as it is designed to estimate risk in adults (age > 20) to predict 10-year risk for myocardial infarction and coronary death. The FRS is calculated

based on six indices: age, gender, total cholesterol, HDL cholesterol, smoker (Y/N), systolic blood pressure, and medications to treat high blood pressure (Y/N). It is one of the most widely validated and cited clinical prediction scores, and although several modifications have been proposed, a recent review of over 1900 studies found that these studies had “flaws in their design, analyses, and reporting that cast some doubt on the reliability of the claims for improved prediction”⁶⁸. The Medical History form will collect the patient data necessary to calculate the FRS score.

- xi. **Physical Activity Readiness Questionnaire (PAR-Q⁶⁹)** is a seven-item, self-report questionnaire to screen individuals for starting an exercise program. In addition to the PAR-Q, an EKG will be required for participants over the age of 40, if clinically indicated, to further minimize potential risks associated with exercising.
- xii. **Credibility/Expectancy Questionnaire (CEQ⁷⁰)** is a 6-item, self-report questionnaire to assess patients' perceptions of and expectations for treatment before the study begins.
- xiii. **Client Satisfaction Questionnaire-8 (CSQ-8⁷¹)** is a reliable and valid self-report of participants' acceptability of treatment. This is an assessment of client/patient satisfaction with their care and perceived quality and tolerability of NEW Tx.
- xiv. **NEW Tx Scale** is a 10-item scale to assess participants' acceptability of NEW Tx. This scale also includes a comments section to solicit unstructured feedback from participants on NEW Tx.

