- iii. **Aim 3: Exploratory Aims (Phase II).** *Hypotheses 3a and 3b:* Between treatment group effects sizes (and 95% CI) will be calculated. To supplement this, Mann-Whitney tests will compare treatment groups on medical burden (as measured by FRS) (*Hypothesis 3a*) and on improvement in symptoms (MADRS, YMRS) and functioning (LIFE-RIFT) (*Hypothesis 3b*) based on change from baseline. *Hypothesis 3c.1:* We will investigate baseline BMI as a potential moderator of treatment response. The focus will be on the magnitude of the effect, not on significance testing. The between treatment group effect sizes (i.e., FRS, MADRS, YMRS, LIFE-RIFT) will be compared with those who have high baseline BMI (> 30) versus low BMI (< 30). *Hypothesis 3c.2:* Mastery of the diet (Nutrition Data System score of food diaries) and exercise (weekly exercise duration from Exercise Questionnaire) modules will mediate the association of NEW Tx and improvement in medical burden (FRS). The

dependent variable will represent change in the FRS score from time of completion of respective module. The mediators will be tested separately. Differential between treatment group effect sizes for those who did and did not master the modules will provide evidence of a mediator of treatment.

C. Rate of Attrition

Some attrition (i.e., 20%) is expected and this can result in bias and reduce power, precision and generalizability⁷⁹. Consistent with the Intent to Treat principle⁸⁰, we will continue with the assessments for the study duration, even among those who fail to comply with the treatment⁸¹. As one aspect of the feasibility study, we will assess the likelihood to attrite using the “Intent to Attend” measure⁷².

D. Power Analysis

The sample sizes for the Phase I and II trials are based primarily on the fundamental aim of this project: feasibility. The N is not based on what is needed for inferential analyses as they are not a fundamental aspect of the design. Power analyses are not indicated for the proposed exploratory analyses. We acknowledge that we will not have sufficient power to detect large effects (e.g., $d = .80$).

IX. REFERENCES

1. Hennekens C. Increasing global burden of cardiovascular disease in general populations and patients with schizophrenia. *Journal of Clinical Psychiatry*. 2007;68(suppl 4):4-7.

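### Hypothesis 3c.2 measures FRS change from module completion, which no TAU participant reaches by Week 20, so the between-arm mediation contrast cannot be derived as written

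*Combined protocol and SAP*

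**What the plan says.** Section VIII.B.iii, Hypothesis 3c.2, proposes that mastery of the diet and exercise modules mediates the effect of NEW Tx on medical burden. Mastery is to be taken from the Nutrition Data System score of the food diaries and from weekly exercise duration on the Exercise Questionnaire. The outcome is defined by one sentence: the "dependent variable will represent change in the FRS score from time of completion of respective module". The decision rule follows: "Differential between treatment group effect sizes for those who did and did not master the modules will provide evidence of a mediator of treatment".

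Four other places bear on whether this outcome can be computed:

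- Section IV.C.x: the FRS uses total and HDL cholesterol, as well as age, gender, smoking, systolic blood pressure and blood-pressure medication.
- Section IV.B: "a fasting blood draw will be conducted at Week 0, Week 10, and Week 20". Table 1 also marks a draw at the Week 32 follow-up. For TAU participants who later take up NEW Tx, "fasting blood draws will be conducted at Weeks 30, Week 40, and Week 52, in addition to the aforementioned draws".
- Section III: "NEW Tx is a flexible modular treatment such that modules are selected based on the needs of the individual". No section gives a week or a criterion for completing a module.
- Section IV.A.ii: TAU is the control, and its participants may choose NEW Tx only once they have completed the first 20 weeks.

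Hypotheses 3a and 3b, in the same paragraph as 3c.2, are analysed as change from baseline.

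**The concern.** A between-arm effect size needs the same outcome in both arms. This outcome starts at an event that only treated participants can have during the randomized comparison. Even for treated participants, the event need not fall in a week when the FRS can be calculated. An analyst following the sentence literally gets no result for 3c.2. An analyst who wants a result must invent a start date for TAU, a mapping from completion to a blood draw for NEW Tx, and an end date for both. Those choices would be made with the data in hand and could give the two arms different lengths of follow-up.

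**Working it through.** The plan states no figure for 3c.2, so there is nothing to reproduce. The check is whether the outcome can be built from the scheduled data.

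**Step 1: control arm.** The outcome needs a module completion time. Section IV.A.ii gives TAU no modules in Weeks 0 to 20, and no substitute index date is stated. The number of TAU participants with a defined outcome in the randomized comparison is therefore zero, whatever the sample size. The mediator data are not the obstacle. The Table 1 footnote keeps TAU food diaries at Weeks 0, 10 and 20, and the Exercise Questionnaire row carries no TAU restriction. What TAU lacks is the outcome's start time and a meaning for mastery.

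**Step 2: NEW Tx arm, start value.** The inputs are the Table 1 visit columns and the draw weeks in section IV.B and Table 1.

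- Post-baseline treatment visits: Weeks 1 to 14, 16, 18 and 20, so 14 + 3 = 17.
- Visits with a draw: Weeks 10 and 20, so 2.
- Visits without a draw: 17 − 2 = 15.
- Visits with a draw and a later draw by Week 20: Week 10 only. A participant completing at Week 20 has only Week 32 afterwards.

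**Step 3: what a substitute rule would do.** The plan states no such rule; these two are illustrations.

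- *Nearest draw.* The distances in weeks from Weeks 1 to 14 to the nearest of Weeks 0, 10 and 20 are 1, 2, 3, 4, 5, 4, 3, 2, 1, 0, 1, 2, 3, 4 (sum 35). For Weeks 16, 18 and 20 they are 4, 2, 0 (sum 6). The mean is 41 / 17 = 2.4 weeks and the maximum is 5.
- *Last earlier draw.* The start value can be up to 9 weeks old (completion at Week 9, draw at Week 0).

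Under either rule the window depends on the participant in NEW Tx, while TAU still needs an arbitrary date.

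**Step 4: other readings of the sentence.**

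- *Change up to completion.* This still needs an FRS at completion and a completion date in TAU.
- *Use Week 32 as the end.* By then TAU participants who opted in are part-way through NEW Tx (Table 2 runs treatment over Weeks 21 to 40), with draws at Weeks 30, 40 and 52.
- *Use module completions after the switch.* These fall outside the randomized comparison.

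**Step 5: the other FRS inputs.** On the source of the FRS data, section IV.C.x says: "The Medical History form will collect the patient data necessary to calculate the FRS score". Table 1 marks that form at Week 0 only, so a scheduled later source for smoking status is not evident. The Clinical Monitoring Form is said to record blood-pressure medication, and blood pressure is among the vitals. Their exact weeks cannot be read reliably from the text copy of Table 1, so nothing here rests on them.

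**The case against.** The best case for the plan has three parts.

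First, this is a sub-hypothesis of an exploratory aim in a feasibility pilot, and section VIII.D says inferential analysis is not central to the design. That stands, and it limits the priority. It excuses low power, but not an outcome that cannot be computed.

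Second, starting the outcome after mastery keeps the mediator before the outcome, which is a sound aim in mediation analysis. That also stands, and the fix should preserve it in at least one analysis.

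Third, the fixed draw weeks alone are not fatal. Diaries are due at least at baseline, Week 10 and Week 20, which are the draw weeks, so diet mastery could be judged at those visits. This weakens the NEW Tx part of the point. It does nothing for TAU, and the plan does not state such a rule.

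A reader might go further than the documents allow in three ways:

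- *That 15 of 17 (88%) is the share of patients without a start value.* It counts visit columns. No section says when participants complete modules.
- *That a known part of the benefit is discarded.* If benefit accrued linearly and the change ended at Week 20, the share captured after completion at week t would be (20 − t) / 20: 50% at Week 10, 20% at Week 16 and 0% at Week 20. Neither condition is in the plan, which gives no end time for 3c.2, and Table 1 has a later draw.
- *That the estimate would be biased toward no effect.* The direction depends on the window chosen for TAU, on any drift in TAU, and on how early and late completers differ. A full 20-week window for a worsening TAU arm against a short NEW Tx window could exaggerate the effect.

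**Conclusion.** The point holds. As written, the 3c.2 outcome is undefined for the whole control arm in Weeks 0 to 20, so the planned between-arm effect sizes by mastery cannot be formed. This follows from sections IV.A.ii and VIII.B.iii alone and needs no assumption. In NEW Tx the start value is observed only if completion coincides with a draw, and completion, the end of the change and the visit mapping are all unspecified. If draws are chosen afterwards, the bias could run either way, and the documents do not allow its size to be estimated. The feasibility aims and Hypotheses 3a and 3b do not depend on this sentence. It should be corrected before analysis, at modest priority.

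**What to change.** Replace the outcome sentence in section VIII.B.iii with wording such as: *The dependent variable is change in FRS from Week 0 to Week 20 in both arms. Change from Week 10 to Week 20 is reported alongside it. The mediators, analysed separately, are change from Week 0 to Week 10 in Nutrition Data System score and in weekly exercise duration, in both arms.* The Week 0 to Week 20 change matches the change from baseline used for 3a. The Week 10 to Week 20 change keeps the mediator before the outcome.

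Replace the sentence comparing those who did and did not master the modules, because mastery has no meaning in TAU. For each mediator, report three things with confidence intervals: the arm difference in the mediator, the association of the mediator with FRS change given arm, and the resulting indirect effect. Present these as descriptive estimates, since randomization does not protect the mediator-to-outcome association.

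Confirm that smoking status, blood pressure and blood-pressure medication are recorded at Weeks 0, 10 and 20 in both arms, and that the Exercise Questionnaire is completed by TAU at Weeks 0 and 10. Confirm also that Week 0 and Week 10 diaries are scored for every participant, because section IV.C.vii provides only for dietitian review of selected diaries.

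**Cost.** The change is to wording, with no new blood draws or visits. If any of these inputs is not already collected or scored, there is a small data-collection or scoring burden. The statistical cost is that in the Week 0 to Week 20 analysis the first 10 weeks of FRS change overlap the mediator window. The Week 10 to Week 20 analysis avoids this, but leaves out FRS change before Week 10.

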- ii. **Phase II:** In this phase, we will pilot test the NEW Tx methods compared to TAU ($n = 60$) to further examine feasibility, to estimate an effect size, and to explore its efficacy for reducing medical burden. TAU will be the control group in the Phase II pilot study as it is the standard treatment in the Massachusetts General Hospital (MGH) Bipolar Clinic and Research Program. Participants randomized to TAU who complete the first 20 weeks of the study will have the option to receive NEW Tx. TAU participants who chose to receive NEW Tx (the waitlist group) will follow the same procedures as the NEW Tx group over an additional 20 weeks such that they will have assessments at Weeks 30, (mid-treatment), 40 (post-treatment), and 52 (follow-up) (see Table 2). For TAU, medication and dosage changes are allowed as long as the change is recommended based on the guidelines and participants remain on a mood stabilizer. Medication changes will be monitored with the Clinical Monitoring Form Medication Module. All participants will have a three-month follow-up visit during which post-treatment measures and assessments will be repeated. Participants will be recruited with the same criteria as the nonrandomized trial, but will be randomized using a 1:1 allocation ratio with a blocking strategy. The assessments will be similar to those used in Phase I. In addition to the study staff utilized in Phase I, clinicians with training in CBT and mood disorders will be added as NEW Tx therapists.

B. Participant Selection and Recruitment

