- xv. **Post-Treatment Questionnaire** is an open-ended, 3 question measure that asks participants to identify aspects of the treatment that were helpful or not helpful and that could be improved.
- xvi. **Intent to Attend⁷²** is a single item that measures participants' intent to attend the next study visit which will be used in part to inform the extent to which attrition is ignorable⁷³.
- xvii. **DXA scans** measure total body composition and fat content using low-dose x-rays.
- xviii. **University of Rhode Island Change Assessment Scale (URICA)** is a 32-item, self-administered measure that is a reliable and valid measure of motivation and intention to change at entrance to treatment.
- xix. **Metabolic Cart Assessment**—Metabolic Cart Assessment—A metabolic cart is an electronic medical tool that is used to measure basal metabolic rate and can be used by medical professionals to determine someone's overall health condition. This test indirectly measures how much energy a person's body uses at rest by measuring the amount of oxygen a person consumes versus the amount of carbon dioxide a person expends.

Table 1. Schedule of Assessments for the NEW Tx and TAU groups

Weeks	0	1	2	3	4	5	6	7	8	9	10	11	12	13	14	16	18	20	32
	Pre										Mid							Post/ET	Follow-Up
MINI	x																		
Medical Hx	x																		
Psychiatric Hx	x																		
Demographics	x																		
PAR-Q	x																		
CGI-BP	x										x							x	x
Blood Draw**	x										x							x	x
Vitals	x									x							x	x	
DXA scan	x																x		
CMF	x									x							x	x	
MADRS	x									x							x	x	
YMRS	x									x							x	x	
LIFE-RIFT	x									x							x	x	
NEW Tx Scale																	x	x	
CEQ	x																		
CSQ-8																	x	x	
URICA	x																x	x	
Met Cart	x																x		
Post-Tx Questionnaire																	x	x	

EQ	x	x	x	x	x	x	x	x	x	x	x	x	x	x	x	x	x	x	x	x	x
Intent-to-Attend†	x	x	x	x	x	x	x	x	x	x	x	x	x	x	x	x	x	x	x	x	
Food Diaries†	x	x ¹	x	x ¹	x	x ¹	x	x ¹													

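### Hypothesis 3c.2: a master/non-master difference in arm effects is not sufficient evidence of mediation, is not necessary either if TAU is also split by mastery, and its outcome is not tied to a time at which FRS is measured

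*Combined protocol and SAP*

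**What the plan says.** Hypothesis 3c.2 (II.B.iii and VIII.B.iii) proposes that mastery of the diet and exercise modules mediates the effect of NEW Tx on FRS. Diet mastery is a Nutrition Data System score of the food diaries; exercise mastery is weekly exercise duration. Each mediator is examined separately. The only criterion is that "Differential between treatment group effect sizes for those who did and did not master the modules will provide evidence of a mediator of treatment".

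The outcome is specified as follows: the "dependent variable will represent change in the FRS score from time of completion of respective module".

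Four other places bear on this:

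- **What FRS needs.** It is calculated "based on six indices: age, gender, total cholesterol, HDL cholesterol, smoker (Y/N), systolic blood pressure", plus blood-pressure medication (IV.C.x). It therefore needs a lipid result.
- **When blood is drawn.** IV.B says "a fasting blood draw will be conducted at Week 0, Week 10, and Week 20"; Table 1 adds a draw at the week-32 follow-up.
- **How modules are given.** In section III, "modules are selected based on the needs of the individual". No length or completion time is stated.
- **What TAU receives.** "Participants randomized to TAU who complete the first 20 weeks of the study will have the option to receive NEW Tx" (IV.A.ii). No module is offered to TAU before week 20.

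**The concern.** Mastery arises after randomisation. Comparing arm effects between masters and non-masters has the same form as the moderator analysis in Hypothesis 3c.1, but there the splitting variable is baseline BMI. Mediation asks something else: does NEW Tx change the behaviour, and does the behaviour in turn change FRS? Nothing in the plan estimates the effect of arm on mastery, the association of mastery with FRS within arm, or an indirect effect.

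The sentence can be worked in two ways. In the **split-both-arms** reading, TAU patients are also classified by their diet and exercise behaviour. In the **common-TAU** reading, NEW Tx masters and non-masters are each compared with all of TAU. At stake is a published statement about mechanism that could be wrong, in a direction that depends on choices the plan leaves open. Section VII lists possible mechanisms of change among the uses of the data.

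**Working it through.** **Inputs.** From the documents: the rule and outcome (VIII.B.iii), 1:1 allocation and n = 60 (IV.A.ii), n = 40 (II), 20% attrition (VIII.C). The plan gives no figure for 3c.2, so there is none to reproduce. Mastery rates, effects and correlations below are all assumptions. Y is FRS change in SD units (negative is better); the contrast is d in masters minus d in non-masters; each scenario has 2,000,000 simulated patients.

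**Step 1: what the contrast estimates.** Write Y = cT + bM + hTM + e, with T the arm and M binary mastery.

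- Split both arms: (c + h) - c = h. The term b, which carries additive mediation, drops out.
- Common TAU: the TAU mean cancels, leaving b + h, a non-randomised comparison within NEW Tx.

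With mastery 70% in NEW Tx and 20% in TAU and b = -0.8, the true indirect effect is -0.8 x (0.70 - 0.20) = -0.40.

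| Scenario | Split both arms | Common TAU |
|---|---|---|
| Full additive mediation (indirect -0.40) | 0.00 | -0.78 |
| Direct effect only (-0.4) | 0.00 | 0.00 |
| Mastery works in NEW Tx only (-0.8) | -0.80 | -0.80 |

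**Step 2: continuous mediator.** NEW Tx raises behaviour by 1 SD and each SD changes Y by -0.5, so the indirect effect is -0.50. At cut-offs -0.5, 0, 0.5, 1 and 1.5 the split-both-arms contrast is -0.19, -0.10, 0.00, +0.10 and +0.20: even its sign follows the cut-off. The common-TAU contrast stays between -0.93 and -0.73.

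**Step 3: signals without mediation.**

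- *Trait modifies the treatment effect, mastery inert, both arms split.* The arm effect is -0.4 - k x trait, and the trait correlates 0.3/0.5/0.7 with mastery. At k = 0.2 the contrast is -0.09/-0.17/-0.23; at k = 0.4 it is -0.18/-0.30/-0.45.
- *Trait is prognostic, treatment wholly inert, common TAU.* If the trait correlates r with behaviour and with FRS improvement, behaviour and Y correlate -r². A median split separates mean behaviour by 2 x √(2/π) = 1.596 SD, so the raw contrast is about -1.596r²: -0.144, -0.399 and -0.782 at r = 0.3, 0.5 and 0.7. Simulated and standardised: -0.15, -0.40 and -0.80. That is about a fifth, a half and all of the -0.78 under full mediation.
- *Same trait, NEW Tx raises behaviour 1 SD but behaviour is inert, both arms split.* Across cut-offs the contrast spans -0.04 to +0.04, -0.11 to +0.12 and -0.24 to +0.24.

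**Step 4: the outcome window.** A change from module completion needs an FRS at completion. TAU has no such time in weeks 0 to 20. In NEW Tx, FRS can be computed from the draws at weeks 0, 10, 20 and 32, and nothing links completion to any of them.

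**Step 5: cell sizes if both arms are split.** TAU completers: 60 x 0.8 / 2 = 24, or 40 x 0.8 / 2 = 16. The chance of at most one TAU master is (1 - p)^n + np(1 - p)^(n-1). For p = 5/10/20% this is 0.661/0.292/0.033 at n = 24 and 0.811/0.515/0.141 at n = 16. With assumed mastery of 60% and 10%, the 95% half-width of the contrast at 48 completers is 1.96 x √(1/14.4 + 1/9.6 + 1/2.4 + 1/21.6) = 1.56 SD; at 32 it is 1.92 SD.

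**Step 6: a path-based alternative.** A model of week-20 FRS on arm, week-10 mediator, their interaction and baseline covariates, including baseline FRS, gives an indirect effect of -0.40 under full mediation and 0.00 with a direct effect only. When mastery works only in NEW Tx it gives -0.40 at the NEW Tx slope, but -0.23 if the interaction is left out. It has two weaknesses of its own:

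- *Reverse causation.* Suppose a direct effect of -0.4 SD by week 10, inert behaviour, and early FRS improvement raising week-10 behaviour by 0.2/0.3/0.5 per SD. Adjusting for baseline FRS only gives a spurious -0.09/-0.13/-0.23; another assumed set-up gave -0.14 to -0.33. Adjusting for week-10 FRS gives 0.00.
- *Confounding.* In the last case of Step 3 it gives -0.08/-0.20/-0.33 if baseline URICA misses the trait, -0.05/-0.12/-0.24 if URICA captures it with reliability 0.5, and -0.02/-0.06/-0.14 with reliability 0.8.

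**The case against.** The strongest defence is that the plan promises only evidence, about a potential mediator, in an exploratory section whose sample size is expressly not set for inference. Evidence need not be proof. TAU patients have no module to master, so the common-TAU reading is at least as natural as splitting both arms, and on it the contrast does respond to mediation (-0.78 against 0.00 for a direct effect only). The full false match needs r = 0.7, and no document supplies any such correlation. An arm-by-mastery interaction can also be a genuine part of mediation, as the third row of the table shows.

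Most of this stands, and it limits the point. A reader might infer that the contrast is never necessary for mediation. The documents do not support that, because they leave the TAU comparison open and the failure is shown only when TAU is split. A reader might also infer that FRS is not measured at module completion in NEW Tx. The documents do not say when completion falls; it could coincide with week 10 or 20. What can be said is that it is not tied to any FRS time point.

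The defence does not rescue the rule itself. The lack of sufficiency holds on both readings, and a larger sample would not cure it.

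**Conclusion.** The statement is wrong as written, with minor consequences. The mastery contrast is not sufficient evidence of mediation on either reading. It is also not necessary if TAU is split: it is then zero under full additive mediation with a binary mediator, and its sign depends on the unstated cut-off with a continuous one. With all of TAU as comparator it responds to mediation, but as a non-randomised contrast within NEW Tx. The logical result in Step 1 needs no numerical input; every size quoted rests on assumed rates, effects and correlations. The outcome window is undefined in TAU and unanchored in NEW Tx.

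Only one exploratory sub-aim is affected. The feasibility aims and sample size do not depend on it, and the documents name no decision that would follow from it.

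It would also be too strong to say that a regression-based mediation analysis removes the difficulty. If URICA misses the shared trait, its false signal (-0.08/-0.20/-0.33) exceeds the largest from splitting both arms (about 0.04/0.12/0.24). Its advantage is that it estimates the quantity the hypothesis is about, with assumptions that can be stated.

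**What to change.** Delete the statement that the mastery split provides evidence of mediation. If the split is shown, state the cut-off and the TAU comparison, and label it descriptive. Then, for each mediator separately:

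1. Report the arm difference in the week-10 mediator, adjusted for its baseline value and baseline URICA.
2. Regress week-20 FRS on arm, week-10 mediator (centred at its TAU mean), arm x mediator, baseline mediator, baseline URICA and week-10 FRS, so that the outcome follows the mediator. Show the version with baseline FRS in place of week-10 FRS as a sensitivity analysis.
3. Give the indirect effect at the TAU slope and at the NEW Tx slope, with bootstrap 95% CIs, labelled exploratory, with no claim of mediation from significance.

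State the limits beside the result:

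- Adjusting for week-10 FRS misses mediation before week 10; adjusting only for baseline FRS is open to reverse causation.
- Confounding remains unless URICA captures the shared trait.
- Behaviour change after week 10 is missed.
- Intervals will be wide. For a true -0.50, the baseline-FRS version had a median CI width at the NEW Tx slope of about 0.89 SD with 48 completers and 1.27 SD with 32. Widths for the week-10 version were not computed.

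The cost is analysis wording, a short program and diary scoring. Table 1, "Schedule of Assessments for the NEW Tx and TAU groups", schedules the Exercise Questionnaire and baseline URICA in both arms, with TAU diaries at weeks 0, 10 and 20. For NEW Tx, III.A says "food diaries are used as needed (at minimum at baseline, week 10, and week 20". Nutrition Data System scoring is already planned; the possible extra work is scoring every week-0 and week-10 diary, since IV.C.vii foresees dietitian review of selected diaries only. No new visit or instrument is needed.
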